	Missing	n
Daily dose for Prednisone	≤ 0.25 mg/kg/d	n/N (XX.XX%)
	0.26 – 0.50 mg/kg/d	n/N (XX.XX%)
	0.51 – 0.75 mg/kg/d	n/N (XX.XX%)
	0.71 – 1 mg/kg/d	n/N (XX.XX%)
	Missing	n
M12	Decreased	n/N (XX.XX%)
	Unchanged	n/N (XX.XX%)
	Increased	n/N (XX.XX%)
	Missing	n
Change from baseline		

The daily dose for Prednisone over time and the change from baseline will be graphically represented by stacked bars.

11.4.2.4 Quality of life assessment

- **FACT-BMT**

Derivation

Derived variables	Definition
Physical well-being subscore at Vi Calculated for Vi = {Baseline, W6, W14, M6, M9, M12}	7 * (Sum of the items GP1 to GP7) / Number of items answered Missing if no item answered
Social/family well-being subscore at Vi Calculated for Vi = {Baseline, W6, W14, M6, M9, M12}	7 * (Sum of the items GS1 to GS7) / Number of items answered Missing if no item answered
Emotional well-being subscore at Vi Calculated for Vi = {Baseline, W6, W14, M6, M9, M12}	6 * (Sum of the items GE1 to GE6) / Number of items answered Missing if no item answered
Functionnal well-being subscore at Vi Calculated for Vi = {Baseline, W6, W14, M6, M9, M12}	7 * (Sum of the items GF1 to GF7) / Number of items answered Missing if no item answered
BMT subscore at Vi Calculated for Vi = {Baseline, W6, W14, M6, M9, M12}	10 * (Sum of BMT1 to BMT4 + Sum of C6 to C7 + Sum of BMT5 to BMT6 + BL4 + BMT8) / Number of items answered Missing if no item answered
Global FACT-BMT score at Vi Calculated for Vi = {Baseline, W6, W14, M6, M9, M12}	The global FACT-BMT score is defined as the sum of all the subscores. Missing if at least one subscore is missing
Subscale score - Change from baseline at Vi Calculated for Vi = {W6, W14, M6, M9, M12} and for physical well-	Subscale score at Vi – Subscale score at baseline Missing if the subscore is missing at Vi and/or baseline

being, family/social well-being, emotional well-being, functional well-being and other concerns subscores	
Global FACT-BMT scale score - Change from baseline at Vi Calculated for Vi = {W6, W14, M6, M9, M12}	Global FACT-BMT score at Vi – Global FACT-BMT score at baseline Missing if the global FACT-BMT is missing at Vi and/or baseline

The following table will be presented:

Variable	Visit	Statistics / Modality	FAS Population (N = XX)
First subscore	Baseline	N (N Missing)	XX (XX)
		Mean ± SD	XX.X ± XX.X
		Median [Min ; Max]	XX [XX ; XX]
		CI 95%	[XX.X ; XX.X]
	W6	N (N Missing)	XX (XX)
		Mean ± SD	XX.X ± XX.X
		Median [Min ; Max]	XX [XX ; XX]
		CI 95%	[XX.X ; XX.X]
	W14	N (N Missing)	XX (XX)
		Mean ± SD	XX.X ± XX.X
		Median [Min ; Max]	XX [XX ; XX]
		CI 95%	[XX.X ; XX.X]
	M6	N (N Missing)	XX (XX)
		Mean ± SD	XX.X ± XX.X
		Median [Min ; Max]	XX [XX ; XX]
		CI 95%	[XX.X ; XX.X]
	M9	N (N Missing)	XX (XX)
		Mean ± SD	XX.X ± XX.X
		Median [Min ; Max]	XX [XX ; XX]
		CI 95%	[XX.X ; XX.X]
	M12	N (N Missing)	XX (XX)
		Mean ± SD	XX.X ± XX.X
		Median [Min ; Max]	XX [XX ; XX]
		CI 95%	[XX.X ; XX.X]
First subscore – Change from baseline	W6	N (N Missing)	XX (XX)
Mean ± SD		XX.X ± XX.X	
Median [Min ; Max]		XX [XX ; XX]	
CI 95%		[XX.X ; XX.X]	

	N (N Missing)	XX (XX)
W14	Mean \pm SD	XX.X \pm XX.X
	Median [Min ; Max]	XX [XX ; XX]
	CI 95%	[XX.X ; XX.X]
	N (N Missing)	XX (XX)
M6	Mean \pm SD	XX.X \pm XX.X
	Median [Min ; Max]	XX [XX ; XX]
	CI 95%	[XX.X ; XX.X]
	N (N Missing)	XX (XX)
M9	Mean \pm SD	XX.X \pm XX.X
	Median [Min ; Max]	XX [XX ; XX]
	CI 95%	[XX.X ; XX.X]
	N (N Missing)	XX (XX)
M12	Mean \pm SD	XX.X \pm XX.X
	Median [Min ; Max]	XX [XX ; XX]
	CI 95%	[XX.X ; XX.X]

This table will be completed for:

- Physical well-being subscore
- Social/family well-being subscore
- Emotional well-being subscore
- Functionnal subscore
- BMT subscore
- FACT-BMT score

Global score and each subscore over time will be graphically represented by boxplots.

The change from baseline over time of the global score and each subscore will be graphically represented by the mean and its associated CI 95%.

- **Lee Symptom Scale**

Derivation

Derived variables	Definition
Skin subscore at Vi Calculated for Vi = {Baseline, W6, W14, M6, M9, M12}	If at least 2 of the following items are answered, Scores are linearly transformed to a 0-100 scale where 0 means all answered items were a "0" and "100" means that all answered items were a "4" Items: Abnormal skin color, Rashes, Thickened skin, Sores on skin and Itchy skin

	Missing otherwise
Eyes and mouth subscore at Vi Calculated for Vi = {Baseline, W6, W14, M6, M9, M12}	If at least 2 of the following items are answered, Scores are linearly transformed to a 0-100 scale where 0 means all answered items were a "0" and "100" means that all answered items were a "4" Items: Dry eyes, Need to use eyedrops frequently, Difficulty seeing clearly, Need to avoid certain foods due to mouth pain, Ulcers in mouth and Receiving nutrition from an intravenous line and feeding tube Missing otherwise
Breathing subscore at Vi Calculated for Vi = {Baseline, W6, W14, M6, M9, M12}	If at least 2 of the following items are answered, Scores are linearly transformed to a 0-100 scale where 0 means all answered items were a "0" and "100" means that all answered items were a "4" Items: Frequent cough, Colored sputum, Shortness of breath with exercise, Shortness of breath at rest and Need to use oxygen Missing otherwise
Eating and digestion subscore at Vi Calculated for Vi = {Baseline, W6, W14, M6, M9, M12}	If at least 2 of the following items are answered, Scores are linearly transformed to a 0-100 scale where 0 means all answered items were a "0" and "100" means that all answered items were a "4" Items: Difficulty swallowing solid foods, Difficulty swallowing liquids, Vomiting and Weight loss Missing otherwise
Muscles and joints subscore at Vi Calculated for Vi = {Baseline, W6, W14, M6, M9, M12}	If at least 2 of the following items are answered, Scores are linearly transformed to a 0-100 scale where 0 means all answered items were a "0" and "100" means that all answered items were a "4" Items: Joint and muscle aches, Limited joint movement, Muscle cramps and Weak muscles Missing otherwise

Energy subscore at Vi Calculated for Vi = {W6, W14, M6, M9, M12}
	
If at least 2 of the following items are answered, Scores are linearly transformed to a 0-100 scale where 0 means all answered items were a “0” and “100” means that all answered items were a “4”
 
Items: Loss of energy, Need to sleep more/take naps and Fevers
 
Missing otherwise

Mental and emotional subscore at Vi Calculated for Vi = {Baseline, W6, W14, M6, M9, M12}
	
If at least 2 of the following items are answered, Scores are linearly transformed to a 0-100 scale where 0 means all answered items were a “0” and “100” means that all answered items were a “4”
 
Items: Depression, Anxiety and Difficulty sleeping
 
Missing otherwise

Global Lee symptom scale score at Vi Calculated for Vi = {Baseline, W6, W14, M6, M9, M12}
	
The global score is defined as the average of subscores, if at least 4 are available.
 
Missing otherwise

Subscale score - Change from baseline at Vi Calculated for Vi = {W6, W14, M6, M9, M12} and for skin, eyes and mouth, breathing, eating and digestion, muscles and joints, energy, mental and emotional subscores
	
Subscale score at Vi – Subscale score at baseline
 
Missing if the subscore is missing at Vi and/or baseline

Global Lee symptom scale score - Change from baseline at Vi Calculated for Vi = {W6, W14, M6, M9, M12}
	
Global Lee score at Vi – Global Lee score at baseline
 
Missing if the global Lee score is missing at Vi and/or baseline

The following table will be presented:

Variable	Visit	Statistics / Modality	FAS Population (N = XX)
First subscore	Baseline	N (N Missing)	XX (XX)
		Mean ± SD	XX.X ± XX.X
		Median [Min ; Max]	XX [XX ; XX]
		CI 95%	[XX.X ; XX.X]
	W6	N (N Missing)	XX (XX)
		Mean ± SD	XX.X ± XX.X
		Median [Min ; Max]	XX [XX ; XX]
		CI 95%	[XX.X ; XX.X]
	W14	N (N Missing)	XX (XX)
		Mean ± SD	XX.X ± XX.X
		Median [Min ; Max]	XX [XX ; XX]
		CI 95%	[XX.X ; XX.X]
	M6	N (N Missing)	XX (XX)
		Mean ± SD	XX.X ± XX.X
		Median [Min ; Max]	XX [XX ; XX]
		CI 95%	[XX.X ; XX.X]
	M9	N (N Missing)	XX (XX)
		Mean ± SD	XX.X ± XX.X
		Median [Min ; Max]	XX [XX ; XX]
		CI 95%	[XX.X ; XX.X]
	M12	N (N Missing)	XX (XX)
		Mean ± SD	XX.X ± XX.X
		Median [Min ; Max]	XX [XX ; XX]
		CI 95%	[XX.X ; XX.X]
First subscore – Change from baseline	W6	N (N Missing)	XX (XX)
		Mean ± SD	XX.X ± XX.X
		Median [Min ; Max]	XX [XX ; XX]
		CI 95%	[XX.X ; XX.X]
	W14	N (N Missing)	XX (XX)
		Mean ± SD	XX.X ± XX.X
		Median [Min ; Max]	XX [XX ; XX]
		CI 95%	[XX.X ; XX.X]
	M6	N (N Missing)	XX (XX)
		Mean ± SD	XX.X ± XX.X
		Median [Min ; Max]	XX [XX ; XX]
		CI 95%	[XX.X ; XX.X]
	M9	N (N Missing)	XX (XX)
		Mean ± SD	XX.X ± XX.X
		Median [Min ; Max]	XX [XX ; XX]

	CI 95%	[XX.X ; XX.X]
M12	N (N Missing)	XX (XX)
	Mean ± SD	XX.X ± XX.X
	Median [Min ; Max]	XX [XX ; XX]
	CI 95%	[XX.X ; XX.X]

This table will be completed for:

- Skin subscore
- Eyes and mouth subscore
- Breathing subscore
- Eating and digestion subscore
- Energy subscore
- Mental and emotional subscore
- Global Lee symptom scale score

Global score and each subscore over time will be graphically represented by boxplots.

The change from baseline over time of the global score and each subscore will be graphically represented by the mean and its associated CI 95%.

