17.2 FACT-BMT

17.2.1 FACT-BMT items

FACT-BMT (4ème Version)

Veuillez indiquer votre réponse en entourant un seul chiffre par ligne et en tenant compte des 7 derniers jours.

	AUTRES SUJETS D'INQUIÉTUDE	Pas du tout	Un peu	Moyennement	Beaucoup	Énormément
BMT1	Je m'inquiète de ne pas pouvoir continuer à travailler (y compris le travail à la maison)	0	1	2	3	4
BMT2	Je me sens distant(e) des autres.....	0	1	2	3	4
BMT3	J'ai peur que la greffe ne réussisse pas.....	0	1	2	3	4
BMT4	Les effets du traitement sont pires que ce que j'imaginais	0	1	2	3	4
C6	J'ai bon appétit.....	0	1	2	3	4
C7	Je suis satisfait(e) de mon apparence physique.....	0	1	2	3	4
BMT5	Je peux me débrouiller seul(e)	0	1	2	3	4
BMT6	Je me fatigue facilement	0	1	2	3	4
BL4	Le sexe m'intéresse.....	0	1	2	3	4
BMT7	J'ai peur de ne plus pouvoir avoir d'enfants	0	1	2	3	4
BMT8	J'ai confiance en mes infirmières(iers).....	0	1	2	3	4
BMT9	Je regrette d'avoir eu une greffe de la moelle osseuse	0	1	2	3	4
BMT 10	J'ai de la mémoire	0	1	2	3	4
Br1	Je suis capable de me concentrer	0	1	2	3	4
BMT 11	J'ai fréquemment des rhumes ou des infections.....	0	1	2	3	4
BMT 12	Je vois trouble.....	0	1	2	3	4
BMT 13	Je suis gêné(e) par un changement de goût des aliments	0	1	2	3	4
BMT 14	J'ai des tremblements	0	1	2	3	4
Br1	J'ai le souffle court.....	0	1	2	3	4
BMT 15	Je suis gêné(e) par des problèmes de peau (éruptions démangeaisons)	0	1	2	3	4
BMT 16	J'ai du mal à aller à la selle	0	1	2	3	4
BMT 17	Ma maladie est une lourde épreuve pour ma famille proche	0	1	2	3	4
BMT 18	Le coût du traitement est un fardeau pour moi et pour ma famille.....	0	1	2	3	4

FACT-BMT (4ème Version)

Vous trouverez ci-dessous une liste de commentaires que d'autres personnes atteintes de la même maladie que vous ont jugés importants. **Veuillez indiquer votre réponse en entourant un seul chiffre par ligne et en tenant compte des 7 derniers jours.**

	BIEN-ÊTRE PHYSIQUE	Pas du tout	Un peu	Moyennement	Beaucoup	Énormément
GP1	Je manque d'énergie.....	0	1	2	3	4
GP2	J'ai des nausées	0	1	2	3	4
GP3	À cause de mon état physique, j'ai du mal à répondre aux besoins de ma famille	0	1	2	3	4
GP4	J'ai des douleurs	0	1	2	3	4
GP5	Je suis incommodé(e) par les effets secondaires du traitement.....	0	1	2	3	4
GP6	Je me sens malade	0	1	2	3	4
GP7	Je suis obligé(e) de passer du temps allongé(e)	0	1	2	3	4

	BIEN-ÊTRE FAMILIAL/SOCIAL	Pas du tout	Un peu	Moyennement	Beaucoup	Énormément
GS1	Je me sens proche de mes amis	0	1	2	3	4

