GS2	Ma famille me soutient moralement.....	0	1	2	3	4
GS3	Mes amis me soutiennent	0	1	2	3	4
GS4	Ma famille a accepté ma maladie	0	1	2	3	4
GS5	Je suis satisfait(e) de la communication avec ma famille au sujet de ma maladie	0	1	2	3	4
GS6	Je me sens proche de mon (ma) partenaire (ou de la personne qui est mon principal soutien).....	0	1	2	3	4
Q1	Quel que soit votre degré d'activité sexuelle en ce moment, veuillez répondre à la question suivante. Si vous préférez ne pas y répondre, cochez cette case  et passez à la section suivante.					
GS7	Je suis satisfait(e) de ma vie sexuelle.....	0	1	2	3	4

FACT-BMT (4ème Version)

Veuillez indiquer votre réponse en entourant un seul chiffre par ligne et en tenant compte des 7 derniers jours.

	BIEN-ÊTRE ÉMOTIONNEL	Pas du tout	Un peu	Moyennement	Beaucoup	Énormément
GE1	Je me sens triste.....	0	1	2	3	4
GE2	Je suis satisfait(e) de la façon dont je fais face à ma maladie	0	1	2	3	4
GE3	Je perds espoir dans le combat contre ma maladie.....	0	1	2	3	4
GE4	Je me sens nerveux (nervouse).....	0	1	2	3	4
GE5	Je suis préoccupé(e) par l'idée de mourir.....	0	1	2	3	4
GE6	Je suis préoccupé(e) à l'idée que mon état de santé puisse s'aggraver.....	0	1	2	3	4

	BIEN-ÊTRE FONCTIONNEL	Pas du tout	Un peu	Moyennement	Beaucoup	Énormément
GF1	Je suis capable de travailler (y compris le travail à la maison)	0	1	2	3	4
GF2	Mon travail (y compris le travail à la maison) me donne de la satisfaction	0	1	2	3	4
GF3	Je suis capable de profiter de la vie.....	0	1	2	3	4
GF4	J'ai accepté ma maladie.....	0	1	2	3	4
GF5	Je dors bien.....	0	1	2	3	4
GF6	J'apprécie mes loisirs habituels.....	0	1	2	3	4
GF7	Je suis satisfait(e) de ma qualité de vie actuelle	0	1	2	3	4

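### The FACT-BMT formulas in SAP 11.4.2.4 show no reversal of negatively worded items and do not point to 17.2.2; applied literally, best and worst global scores differ by 12 points instead of 148

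*SAP*

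**What the plan says.** SAP 11.4.2.4 gives five subscore formulas of the same form:

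- Physical: "7 * (Sum of the items GP1 to GP7) / Number of items answered"
- Social/family: "7 * (Sum of the items GS1 to GS7) / Number of items answered"
- Emotional: "6 * (Sum of the items GE1 to GE6) / Number of items answered"
- Functional: "7 * (Sum of the items GF1 to GF7) / Number of items answered"
- BMT: "10 * (Sum of BMT1 to BMT4 + Sum of C6 to C7 + Sum of BMT5 to BMT6 + BL4 + BMT8", closed and divided by the number of items answered

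Then: "The global FACT-BMT score is defined as the sum of all the subscores". A subscore is set to missing only when none of its items has an answer; the global score is missing if any subscore is.

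SAP 17.2.1 reproduces the French questionnaire. Every item is answered from 0 (not at all) to 4 (extremely). Some items are complaints, such as GP6, "Je me sens malade" (I feel ill). Others are positive, such as GF3, "Je suis capable de profiter de la vie" (I am able to enjoy life).

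SAP 17.2.2 is titled as the place for the details of the FACT-BMT calculation. In the supplied text only its heading appears, directly before 17.3. The visible text of the two documents nowhere mentions reversing items or says whether a high FACT-BMT score is good or bad. For the Lee Symptom Scale, SAP 17.3 does state the direction.

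**The concern.** A sum of items is a usable score only if all its items point the same way. Here the physical subscore would rise as the patient gets worse, the social and functional subscores would rise as the patient gets better, and the emotional and BMT subscores would mix both directions. Adding the five then sets losses against gains.

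Improving quality of life on FACT-BMT is a named secondary objective (Protocol 2.2, SAP 8.1.2). SAP 11.4.2.4 tabulates each subscore and the global score at every visit, with change from baseline and 95% confidence intervals. If the formulas are programmed as they stand, a real fall in symptoms lowers the global score, and a change from baseline in that score has no clear meaning.

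The missing-item rule is a second, smaller weakness. One answered item is multiplied up to the full subscale.

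**Working it through.** **Inputs.** The formulas are those of SAP 11.4.2.4. Item directions are read from the wording in SAP 17.2.1, not from an outside scoring manual. The plan gives no FACT-BMT range or worked score, so there is no figure to reproduce. As a check on the reading, the multipliers 7, 7, 6, 7 and 10 equal the numbers of items in the five formulas.

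| Subscale | Items | Negative | Positive |
|---|---|---|---|
| Physical | 7 | 7 (GP1-7) | 0 |
| Social/family | 7 | 0 | 7 (GS1-7) |
| Emotional | 6 | 5 (GE1, GE3-6) | 1 (GE2) |
| Functional | 7 | 0 | 7 (GF1-7) |
| BMT | 10 | 5 (BMT1-4, BMT6) | 5 (C6, C7, BMT5, BL4, BMT8) |
| Total | 37 | 17 | 20 |

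**Literal scores, all items answered.** With complete answers the multiplier cancels the divisor, so each subscore is the raw sum.

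In the best state every positive item is 4 and every negative item is 0. In the worst state this is turned round. Each subscore is therefore 4 × (number of positive items) at best and 4 × (number of negative items) at worst.

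| | Physical | Social | Emotional | Functional | BMT | Global |
|---|---|---|---|---|---|---|
| Best, as written | 0 | 28 | 4 | 28 | 20 | 80 |
| Worst, as written | 28 | 0 | 20 | 0 | 20 | 68 |
| Best, with 4 - response | 28 | 28 | 24 | 28 | 40 | 148 |
| Worst, with 4 - response | 0 | 0 | 0 | 0 | 0 | 0 |

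The contrast between the extremes is 80 - 68 = 12 points as written, against 37 × 4 = 148 with reversal: 12/148, or about 8%.

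**One-level improvement on every item.** As written: 20 - 17 = +3 points. With reversal: +37 points.

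**Cancellation.** If all seven physical and all seven functional items improve by one level, the subscores change by -7 and +7, and the global change is 0. With reversal it is +14.

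**Prorating from one answer.** A patient who answers a single physical item with 4 gets 7 × 4 / 1 = 28, the maximum of that subscale. The Lee scoring rules in SAP 17.3 require 50% of a subscale's items.

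**The case against.** The strongest reply is that the deciding page is not visible. SAP 17.2.2 has the right title for a reversal key, and the table of contents places it on page 118 with 17.3 on page 119, so it probably has content that was lost when the PDF was read. Silence in 11.4.2.4 is also weak evidence of absence. For the Lee scale too, the direction of scoring stands only in the appendix and the body does not cite it. This stands. A reader might infer that the plan has no reversal rule at all, and the documents do not support that. It is also possible that items are reversed in the database before scoring, though no visible text says so.

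A reader might also infer that the global score cannot tell the best state from the worst. That goes too far: it gives 80 and 68. Only the BMT subscore is identical in the two states. The physical, social and functional subscores each run in one direction and are tabulated separately, so they can be interpreted unreversed, provided the direction is stated.

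On missing items, it is fair to say that the 50% rule comes from the Lee appendix. The Lee derivation in the body of 11.4.2.4 asks only for two answered items, which is 2 of 5 (40%) for skin and 2 of 6 (33%) for eyes and mouth. Even so, both Lee rules ask for more than one answer, and the FACT-BMT rule does not.

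Finally, the stakes are limited. Quality of life is analysed descriptively (Protocol 9.1.2), and Protocol 9.2 calls patient-reported outcomes exploratory.

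What the reply does not remove is that the formulas in 11.4.2.4 are detailed enough to be programmed on their own. They select ten of the listed BMT items and fix the multipliers, yet give no direction and no pointer to 17.2.2. Nor can agreement between body and appendix be taken for granted, since for the Lee scale they differ.

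**Conclusion.** The point holds as a defect of the formulas in SAP 11.4.2.4, not as a finding that the whole plan lacks a reversal key. Taken literally, they shrink the best-to-worst contrast in the global score from 148 points to 12, make the BMT subscore 20 at both extremes, and let equal physical and functional gains cancel. The size rests on two assumptions: that item directions follow the French wording in 17.2.1, and that raw responses enter the formulas. If 17.2.2 already holds the reversal and the programmer applies it, the numerical problem disappears and only a missing cross-reference remains.

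The rule that allows a subscore from one answered item is explicit in 11.4.2.4. It is worth changing unless 17.2.2 already sets a stricter minimum.

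Both matters concern a descriptive secondary endpoint. No hypothesis test, decision rule or sample size depends on FACT-BMT.

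**What to change.** 1. In SAP 11.4.2.4, state that GP1-7, GE1, GE3-6, BMT1-4 and BMT6 are scored as 4 - response before summing, and that a higher score means better quality of life. Alternatively, cite 17.2.2 there, after confirming that it contains this reversal.
2. Replace the missing-item rule with a minimum of at least 50% of a subscale's items answered before prorating, in line with SAP 17.3. In practice that is 4 of 7, 3 of 6 and 5 of 10.

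The cost of the first change is a line of SAP text and a small programming change, or only the cross-reference if the key already exists and is already programmed. The second costs a few more missing subscores, and with them some missing global scores, because the SAP sets the global score to missing when any subscore is missing. No data collection changes.

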17.2.2 Details of FACT-BMT calculation

17.3 LEE SYMPTOM SCALE

The Lee Chronic GVHD Symptom Scale is a 30 item instrument with 7 subscales (skin, eyes, mouth, lung, nutrition, energy and psych) containing 2-7 items. Response options for "let us know if you have been bothered by any of the following in the past month" range from 0-4 (Not at all, Slightly, Moderately, Quite a bit, Extremely). Some investigators have used the scale in reference to the past 7 days. (Lee SJ, Cook EF, Soiffer R, Antin JH. Development and validation of a scale to measure symptoms of chronic graft-versus-host disease. *Biol Blood Marrow Transplant* 2002; 8:444-452)

Subscale name	Number of items	Items
Skin	5	a. Abnormal skin color b. Rashes c. Thickened skin d. Sores on skin e. Itchy skin
Eye	3	f. Dry eyes g. Need to use eyedrops frequently h. Difficulty seeing clearly
Mouth	2	i. Need to avoid certain foods due to mouth pain j. Ulcers in mouth
Lung	5	l. Frequent cough m. Colored sputum o. Shortness of breath at rest p. Need to use oxygen aa. Fevers
Nutrition	5	k. Receiving nutrition from an intravenous line or feeding tube

		q. Difficulty swallowing solid foods r. Difficulty swallowing liquids s. Vomiting t. Weight loss
Energy	7	n. Shortness of breath with exercise u. Joint and muscle aches v. Limited joint movement w. Muscle cramps x. Weak muscles y. Loss of energy z. Need to sleep more/take naps
Psych	3	bb. Depression cc. Anxiety dd. Difficulty sleeping

Bold indicates items that are scored under a different subscale than where they are located

Scoring rules:

1. Note that the subscales do not conform exactly to the categories in the patient survey.
2. Subscales may be scored if 50% or more of the items in the subscale are completed.
3. Scores are linearly transformed to a 0-100 scale where 0 means all answered items were a "0" and "100" means that all answered items were a "4"
4. Missing items are not included in the scoring.
5. The summary score is the average of the subscale scores, as long as 4 or more subscales are available.
6. Higher scores indicate more severe symptoms.
7. A clinically meaningful difference for each subscale or the summary score is considered to be half a standard deviation of the baseline score for the population, based on the distribution method of determining clinically meaningful changes.

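### SAP 11.4.2.4 scores the Lee Symptom Scale by questionnaire heading, which contradicts the item map and completeness rule in the SAP's own scoring appendix (17.3)

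*SAP*

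**What the plan says.** SAP 11.4.2.4 defines seven subscores that follow the headings of the patient form in Protocol Appendix 10: skin, eyes and mouth, breathing, eating and digestion, muscles and joints, energy, mental and emotional. The eyes-and-mouth subscore starts "Items: Dry eyes, Need to use eyedrops frequently, Difficulty seeing clearly, Need to avoid certain foods due to mouth pain, Ulcers in mouth" and ends with the item on intravenous or tube feeding. The energy subscore has three items: "Items: Loss of energy, Need to sleep more/take naps and Fevers". Every subscore uses the same completeness rule: "If at least 2 of the following items are answered, Scores are linearly transformed to a 0-100 scale". For the total: "The global score is defined as the average of subscores, if at least 4 are available".

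SAP 17.3 sets out the scoring of the same 30-item instrument with seven subscales named skin, eye, mouth, lung, nutrition, energy and psych. Its energy subscale begins "n. Shortness of breath with exercise u. Joint and muscle aches v. Limited joint movement w. Muscle cramps x. Weak muscles" and adds the two tiredness items, seven in all. It cautions: "Note that the subscales do not conform exactly to the categories in the patient survey". Its completeness rule is "Subscales may be scored if 50% or more of the items in the subscale are completed". The total is again the mean of the subscales, with at least four available.

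Neither document says that the regrouping in 11.4.2.4 is deliberate or which section governs.

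**The concern.** The two sections give different scores for the same answers. Section 11.4.2.4 shares the appendix's linear 0-100 transformation and its rule of averaging at least four subscales, so the appendix looks like its source, yet it uses the printed headings that the appendix says are not the subscales. This looks like a slip rather than a choice.

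Improving quality of life on this scale is a secondary objective (SAP 8.1.2), and Protocol 9.2 says that changes in chronic GvHD severity were best detected by changes in this scale. If the score is built on another item map, that argument no longer clearly supports it, and the Energy results cannot be compared with results for the subscale that 17.3 calls Energy.

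Two clerical gaps sit in the same place. Baseline is missing from the energy visit list. Muscles and joints is derived but appears in neither the list of scores to tabulate nor the figure list in SAP 14.2. Read literally, Energy has no baseline score and hence no change from baseline, and the baseline global score averages six subscores against seven later.

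**Working it through.** **Inputs.** Item letters a to dd come from Protocol Appendix 10 and SAP 17.3; the groupings come from SAP 11.4.2.4 and 17.3.

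| SAP 11.4.2.4 | Items | n | SAP 17.3 | Items | n |
|---|---|---|---|---|---|
| Skin | a-e | 5 | Skin | a-e | 5 |
| Eyes and mouth | f-k | 6 | Eye | f-h | 3 |
| Breathing | l-p | 5 | Mouth | i, j | 2 |
| Eating and digestion | q-t | 4 | Lung | l, m, o, p, aa | 5 |
| Muscles and joints | u-x | 4 | Nutrition | k, q-t | 5 |
| Energy | y, z, aa | 3 | Energy | n, u-z | 7 |
| Mental and emotional | bb-dd | 3 | Psych | bb-dd | 3 |

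**Stated structure.** 17.3 describes 30 items in seven subscales of 2 to 7 items. Its own map reproduces this: 5+3+2+5+5+7+3 = 30, range 2 to 7. The 11.4.2.4 map also uses 30 items (5+6+5+4+4+3+3), but its range is 3 to 6. Only Skin and Mental/Psych have the same items, so five of seven subscales differ.

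**Item weights in the global score.** With all items answered, each subscale is its mean item × 25 and the global score is the mean of seven subscales. The weight of an item is therefore 1/(7 × n).

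| Items | 11.4.2.4 | 17.3 | Ratio |
|---|---|---|---|
| f-h | 1/42 = 2.4% | 1/21 = 4.8% | 0.50 |
| i, j | 1/42 = 2.4% | 1/14 = 7.1% | 0.33 |
| k | 1/42 = 2.4% | 1/35 = 2.9% | 0.83 |
| n | 1/35 = 2.9% | 1/49 = 2.0% | 1.40 |
| q-t | 1/28 = 3.6% | 1/35 = 2.9% | 1.25 |
| u-x | 1/28 = 3.6% | 1/49 = 2.0% | 1.75 |
| y, z | 1/21 = 4.8% | 1/49 = 2.0% | 2.33 |
| aa | 1/21 = 4.8% | 1/35 = 2.9% | 1.67 |

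That is 3+2+1+1+4+4+2+1 = 18 items with a different weight. The other 12 (a-e, l, m, o, p, bb-dd) agree.

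**Effect on scores** (higher is worse; complete items).

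- One point better on f-j only, global score: 11.4.2.4 gives −25 × (5/6)/7 = −2.98; 17.3 gives −(25+25)/7 = −7.14. The ratio is 2.4.
- One point better on u-z only, global score: −(25 + 25 × 2/3)/7 = −5.95 against −25 × (6/7)/7 = −3.06.
- Energy subscore, one point better on u-x: 0 against −25 × 4/7 = −14.3. One point better on y and z: −25 × 2/3 = −16.7 against −25 × 2/7 = −7.1.
- Largest gap for identical answers: the sum of the positive weight differences, 3/42 + 4/42 + (1/35 − 1/42) = 17.1%. It occurs with f-k at 4 and all else 0: 100/7 = 14.3 against (100+100+20)/7 = 31.4.
- Opposite movement (eye items one point better, u-x one point worse): −1.79 + 3.57 = +1.79 (after rounding) against −3.57 + 2.04 = −1.53, so the sign reverses.

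**Completeness.** Half the items, rounded up, means 3, 2, 1, 3, 3, 4 and 2 answered items for the 17.3 subscales in table order. Skin shows the conflict by itself: the same five items, but 2 answered (40%) suffice in 11.4.2.4 and 3 are needed in 17.3. Only Mental/Psych agrees on both items and rule.

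**Meaningful change.** 17.3 says that a meaningful difference "is considered to be half a standard deviation of the baseline score for the population". The f-j change would count as meaningful under 17.3 but not under 11.4.2.4 if the baseline SD lay between 2 × 2.98 = 6.0 and 2 × 7.14 = 14.3. The documents give no SD, so this range is an assumption, and it uses one SD for both maps.

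**The case against.** The textual conflict is not in dispute; its importance is.

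- **Selected patterns.** The examples confine change to items where the maps diverge. Both sets of weights sum to 1, so one point better on all 30 items gives −25 under either map, and change in the 12 equally weighted items makes no difference. Assuming equal item variances and a common inter-item correlation r, which the documents do not give, the two global scores correlate at 0.88, 0.97 and 0.99 for r = 0, 0.1 and 0.3. This stands: the 17.1-point gap is an extreme, and the factor of 2.4 is for equal change across f-j only (2 for eye items alone, 3 for mouth items alone). A high correlation does not help the subscale tables, however, where Energy is a different quantity.
- **Half-SD rule.** No planned table or figure classifies changes by it. This also stands; the SD range is only illustrative.
- **No ambiguity for the programmer.** The 11.4.2.4 derivations are explicit, and the table and figure lists use its names. That makes divergent programming less likely, but it also means the reported scores will be the ones that depart from the appendix.
- **Completeness.** On 11.4.2.4's own subscale sizes, the 2-item rule is looser than 50% only for skin, eyes and mouth, and breathing, and it matters only with missing items. Correct.
- **Clerical gaps.** The change-from-baseline row names energy and muscles and joints, the table has a Baseline row, and each subscore is to be plotted. A careful programmer would probably fill both gaps.
- **Low stakes.** Protocol 9.1.2 makes the quality-of-life analysis descriptive, and Protocol 9.2 calls patient-reported outcomes exploratory and keeps them out of response evaluation. This stands and limits the priority.

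**Conclusion.** The concern holds. As written, the SAP gives two incompatible scorings of one instrument: five of seven subscales differ in content, a sixth (Skin) differs in its completeness rule, and 18 of 30 items differ in global weight. The counts are exact; the weights assume all items and all seven subscales are available. The size of the difference in this trial depends on which symptoms change. It is nil for uniform change, 2.98 against 7.14 points in the eye-and-mouth example, and 17.1 points at most. A reversal of sign needs differently weighted items to move in opposite directions; how often that would happen cannot be known from the documents, and a change of 1.79 points is below half an SD once the SD exceeds 2 × 1.79 = 3.6 (an assumed threshold). The primary response analysis is untouched. This should be corrected because the plan would otherwise report subscale and global scores that are not the ones its scoring appendix defines.

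**What to change.** In SAP 11.4.2.4, replace the Lee derivation with the 17.3 item map. Score a subscale when at least half its items are answered: 3 for Skin, 2 for Eye, 1 for Mouth, 3 for Lung, 3 for Nutrition, 4 for Energy and 2 for Psych. Keep the global score as the mean of at least four subscales, and derive everything at every visit including Baseline. Align the list of tabulated scores in 11.4.2.4 and the figure list in SAP 14.2 with those seven subscales, which also removes both clerical gaps.

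If the heading-based grouping was intended, say so, label it as a non-standard score, and report the 17.3 score beside it.

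The cost is one derivation table, two output lists and the scoring program. All 30 items are already collected.
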